10.7.1 Subject Global Impression

The SGI ([Farrar, 2001](#)) is a 7-point scale on which the patient rates their global impression of the effects of a study treatment (1 = terrible to 7 = delighted). The SGI will be assessed by the patient or the patient's parent/guardian/caregiver if the patient is unable to complete the SGI. The SGI has demonstrated concordance with the physician's assessment of improvement ([Dodick, 2007](#)). Instructions for the SGI are provided in [Appendix 1](#) and the CMS-001 Study Reference Manual.

10.7.2 Motor Function Measure

The standard MFM 32 ([Bérard, 2005](#)) evaluates the severity and progression of motor function and is applicable to all degrees of disease severity, in both ambulant and nonambulant patients. It is not, however, well suited as an outcome measure in young children because of the time required to complete the MFM and difficulty in completion in terms of childrens' cognitive and motor development. A short-form (MFM 20) ([de Lattre, 2013](#)) will be used in this study for patients 2 years up to 7 years of age, with each of 20 items scored on a 4-point Likert scale (based on patient's best abilities without assistance): standing and transfers (8 items); axial and proximal motor function (8 items); and distal motor function (4 items). Total MFM 20 score ranges from 0 to 60. The MSM 32 will be used for patients 7 years of age and older, with each of 32 items scored on a 4-point Likert

 Catalyst <small>pharmaceuticals</small>	CMS-001 Version Amendment 5	Page 54
---	---------------------------------------	----------------

scale (based on patient's best abilities without assistance): standing and transfers (13 items), axial and proximal motor function (12 items), and distal motor function (7 items). Total MFM 32 score ranges from 0 to 96. Higher MFM 20 or 32 scores indicate more functional improvement.

MFM 20 or 32 will be administered at the protocol specified time points by the same well trained evaluator throughout the study. Instructions for conducting the MFM 20 and MFM 32 are provided in [Appendix 2](#) and [Appendix 3](#), respectively, and in the CMS-001 Study Reference Manual.

10.7.3 Clinical Global Impression Scales

The CGI score is a 2-part observer-rated instrument that assesses 1) severity of the patient's disease (CGI-S) at a given point in time and 2) change from baseline (CGI-I). This instrument is widely used and well validated ([Busner, 2009](#)). The investigator will complete the 7-point CGI-S based on his/her experience of severity in the CMS population as a whole as the point of reference. Instructions for the CGI-S are contained in [Appendix 4](#) and the CMS-001 Study Reference Manual.

The CGI-I captures the investigator's global impression of the patient's improvement or worsening from baseline status. The 7-point scale is scored by the investigator based on changes in symptoms, behavior, and functional abilities. Instructions for the CGI-I are contained in [Appendix 5](#) and the CMS-001 Study Reference Manual.

10.7.4 Stimulated Single Fiber Electromyogram

Stimulated single fiber EMG is a method to assess the integrity of the neuromuscular junction. The principle of stimulated single fiber EMG is to measure the time variability of the muscle fiber action potentials as they are generated by the discharges of the motor neuron (SFEMG using voluntary activation) versus the variability of a single muscle fiber potential (SFEMG using motor axonal stimulation). In infants, young children, or patients having difficulty in making a controlled activation, stimulated jitter analysis is preferable. From a technical standpoint, facial muscles such as the frontalis and orbicularis oculi are the easiest to record by stimulating the distal branch of the facial nerve supplying them with a monopolar needle electrode. The latter has less associated stimulation artifact and better control of the stimulating impulse. Since the recordings are made with a disposable concentric needle electrode, the term "jitter analysis" is preferred as being semantically more correct than single fiber EMG. Stimulated jitter analysis will be performed by a certified electromyographer. Local anesthetic agent will be applied to the site of needle electrode

 Catalyst <small>pharmaceuticals</small>	CMS-001 Version Amendment 5	Page 55
---	---------------------------------------	----------------

examination 30 minutes before the procedure. Not all patients can tolerate the procedure so this test is optional.

10.7.5 Slurp Test

Patient's with neuromuscular disorders experience increasing weakness of bulbar-innervated muscles that may result in aspiration or catastrophic airway compromise. The "Slurp" test is a non-invasive way of assessing bulbar function (Hudspeth 2006), particularly in children. Four ounces (120 mL) of water is placed in a cup. The patient is instructed to drink the entire contents of the cup through a standard flex straw as quickly as possible, making a loud slurping sound at the end. The duration of time from the start of drinking the water to the slurp sound will be measured. This test is optional. Slurp tests will be initiated during the up-titration phase by parents or investigators until reliable performance is achieved, thereafter only at identified places in the protocol timeline.

11 REPORTING ADVERSE EVENTS

11.1 Adverse Events

For this protocol, a reportable AE is any untoward medical occurrence (e.g. sign, symptom, illness, disease or injury) in a patient administered the IP or other protocol-imposed intervention, regardless of attribution. This includes:

- AEs not previously observed in the patient that emerge during the course of the study.
- Pre-existing medical conditions judged by the investigator to have worsened in severity or frequency or changed in character during the study.
- Complications that occur as a result of non-drug protocol-imposed interventions.

An adverse drug reaction is any AE for which there is a reasonable possibility that the IP caused the AE. "Reasonable possibility" means there is evidence to suggest a causal relationship between the IP and the AE.

Whenever possible, it is preferable to record a diagnosis as the AE term rather than a series of terms relating to a diagnosis.

The study period during which all non-serious AEs will be reported begins after informed consent is obtained and the first administration of study drug through the last visit (Study Day 29) or at the early termination visit. After informed consent but prior to initiation of study treatment, only SAEs associated with any protocol-imposed interventions will be reported. The criteria for determining, and the reporting of SAEs is provided in Section [11.2](#).

The investigator should follow all unresolved AEs until the events are resolved or stabilized, the patient is lost to follow-up, or it has been determined that the study treatment or participation is not the cause of the AE. Resolution of AEs (with dates) should be documented on the appropriate CRF page(s) and in the patient's medical record.

The investigator responsible for the care of the patient or qualified designee will assess AEs for severity, relationship to IP, and seriousness (refer to Section 11.2 for SAE definition). Severity (as in mild, moderate or severe headache) is not equivalent to seriousness, which is based on patient/event outcome or action criteria usually associated with events that pose a threat to a patient's life or functioning. Seriousness (not severity) serves as a guide for defining regulatory reporting obligations.

The investigator will determine the severity of each AE using the following Common Terminology Criteria for Adverse Events (CTCAE) v 4 grades defined in [Table 7](#) (the event will be recorded on the source documents and AE CRF) ([Appendix 5](#)). Events that are CTCAE grades 4 and 5 are serious events and require completion of both an SAE form and AE CRF. Adverse events that do not have a corresponding CTCAE term will be assessed according to the general guidelines for grading used in the CTCAE v4 as stated below.

Table 7. Categories of Severity for CTCAE Criteria

Severity	Description	
Grade 1	Mild; asymptomatic or mild symptoms; clinical or diagnostic observations only; intervention not indicated.	
Grade 2	Moderate; minimal, local or noninvasive intervention indicated; limiting age-appropriate instrumental ADL*.	
Grade 3	Severe or medically significant but not immediately life-threatening; hospitalization or prolongation of hospitalization indicated; disabling; limiting self care ADL**.	
Grade 4	Life-threatening consequences; urgent intervention indicated.	Note: Grade 4 and 5 adverse events should always be reported as serious adverse events
Grade 5	Death related to AE.	

Activities of Daily Living (ADL)

* Instrumental ADL refer to preparing meals, shopping for groceries or clothes, using the telephone, managing money, etc.

** Self care ADL refer to bathing, dressing and undressing, feeding self, using the toilet, taking medications, and not bedridden.

The investigator will suggest the relationship of an AE to the IP and will record it on the source documents and AE CRF, using the relationship categories defined in [Table 8](#).

Table 8. Description of Relationship to Adverse Event Categories

Relationship Category	Description
Not Related	Exposure to the IP has not occurred OR The administration of the IP and the occurrence of the AE are not reasonably related in time OR The AE is considered likely to be related to an etiology other than the use of the IP; that is, there are no facts [evidence] or arguments to suggest a causal relationship to the IP.
Possibly Related	The administration of the IP and the occurrence of the AE are reasonably related in time AND The AE could be explained equally well by factors or causes other than exposure to the IP.
Probably Related	The administration of IP and the occurrence of the AE are reasonably related in time AND The AE is more likely explained by exposure to the IP than by other factors or causes.

In order to classify AEs and diseases, preferred terms will be assigned by the sponsor to the original terms entered in the eCRF, using Medical Dictionary for Regulatory Activities (MedDRA) terminology.

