The only SAEs reported in the study were minor, isolated, and reversible increases in aspartate aminotransferase (AST) and alanine aminotransferase (ALT), which occurred in a single patient after administration of 20 mg amifampridine base. Aside from this 1 patient, no other laboratory abnormalities were observed. No electrocardiogram (ECG) abnormalities were observed. No deaths occurred in the DAPSEL study.

A Phase 1 study (LMS-001) in healthy volunteers evaluated whether food consumption significantly affected the bioavailability of amifampridine phosphate tablets. This was an open-label, randomized, single-dose, 2-treatment, 2-period crossover design in 46 healthy

volunteers. Each patient received 20 mg amifampridine phosphate on 2 occasions, once fasting and once after consumption of a standard high fat breakfast. The 2 single 20 mg doses of amifampridine phosphate were administered 6 days apart. Data indicate that taking amifampridine with food reduces exposures determined by C_{max} (maximum serum levels) by approximately 40% and AUC by approximately 20%. In addition, the time to maximum serum concentrations (T_{max}) was increased 2-fold from approximately 38 minutes (fasted) to 78 minutes (fed). The drug was well tolerated with no serious adverse events and only 1 severe event, an episode of gastroenteritis unrelated to amifampridine. The most common adverse events occurring in $\geq 10\%$ of patients were: oral paresthesia (20 patients; 43%), peripheral paresthesias (12; 26%), dizziness (5; 11%), headache (5; 11%), and oral hypoesthesia (5; 11%). Abdominal pain, nausea, peripheral paresthesias, dizziness, and headache were more commonly reported by patients following administration of amifampridine phosphate in the fasted state; therefore, administration with food is recommended based on the current study.

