8.5 Overall Risks and Benefits

Data on amifampridine treatment in 1,454 patients or healthy volunteers support the favorable safety profile of amifampridine (both base and phosphate formulations) at doses up to 80 mg per day. Current data demonstrate that amifampridine phosphate salt has an acceptable tolerability profile with a positive risk-benefit in patients treated with amifampridine.

Risks of of study involvement have been minimized by:

- 1. Patients entering the study may already be on some formulation of 3,4-diaminopyridine and have demonstrated tolerability or;**
- 2. Patients naïve to the medication are titrated to a tolerable and effective dose with open-label medication, under the observation of the Investigator. Thus, the development of adverse events or lack of efficacy is monitored by the Investigator during the step-wise titration and study medication dose can be reduced or discontinued at any point in the titration for either safety or lack of efficacy.**

The pharmacokinetic half-life of amifampridine phosphate is short (1.8 hours), therefore discontinuation of medication will quickly terminate the effects, and mitigate adverse reactions.

This is a withdrawal study design looking at patient worsening on placebo; which is possible due to the short half-life of amifampridine phosphate. Therefore, patients must demonstrate a level of efficacy during the open-label titration period. This further reduces patient risk, by not continuing an experimental medication in patients who fail to demonstrate a benefit.

During the placebo withdrawal period, patients who deteriorate to a point that the Investigator assess to be lower than their baseline, open-label amifampridine phosphate is provided as to rescue the patient.

Refer to the Firdapse Investigator Brochure (February, 2015) for further information on benefit/risk of amifampridine.

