9 STUDY OBJECTIVES

9.1 Primary Objectives

The primary objectives of the study are:

- To characterize the overall safety and tolerability of amifampridine phosphate compared with placebo in patients with CMS; and
- To assess the clinical efficacy of amifampridine phosphate compared with placebo in patients with CMS, based on improvement in subject global impression (SGI) and motor function measure (MFM 20 or 32) scores.

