15.3 Adverse Events

All treatment-emergent adverse events (TEAEs) will be summarized by the treatment at the time of onset. Counts and percentages will be presented by treatment for each observed system organ class (SOC) and preferred term (PT) as defined in MedDRA. Summaries by level of severity and relationship to treatment will be presented by treatment at the time of occurrence. Listings of all deaths, SAEs, and discontinuations due to AE will be provided.

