5.0 Analysis of Safety

The following describes the statistical analysis of safety data.

Adverse Events

Prior to analysis, all AEs will be coded using the Medical Dictionary for Regulatory Activities (MedDRA). A treatment-emergent adverse event (TEAE) is any AE that occurs after the start of treatment. All TEAEs will be summarized by the treatment at the time of onset. Counts and percentages will be presented by treatment for each observed system organ class (SOC) and preferred term (PT) as defined in MedDRA. Summaries by level of severity and relationship to treatment will be presented by treatment at the time of occurrence. Listings of all deaths, serious AEs (SAEs), and discontinuations due to AE will be provided.

An overall summary table will provide the highest relationship and maximum severity observed per subject, as well as the counts of patients who: discontinued early due to an AE, experienced death, or had at least one SAE.

Laboratory Tests

For each laboratory parameter, descriptive statistics will be presented for the observed value and change from baseline (CFB) by treatment, where CFB is the change from the previous assessment. The frequency and percentage of patients who experience

abnormal (i.e. outside of reference ranges) laboratory values will be presented by treatment and time point.

Concomitant Medications

A table of the WHO-coded medications will be constructed by treatment given in the study period (amifampridine or placebo) and overall with medications summarized by level 4 Anatomical Therapeutic Chemical (ATC) term and Preferred Term. The number and percent of patients on each drug will be summarized. A data listing for all concomitant medications will be provided.

Vital Signs

Summary statistics (mean, median, sample size, standard deviation, minimum, and maximum) will be computed on the raw and change from baseline values for each vital sign parameter by time point, for each treatment. The screening time point will serve as baseline. If there are multiple vital signs taken at any time point, then the latest set of vital signs will be used for the analysis. All vital sign data will be listed.

ECG Results

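### Adverse events are tabulated only by treatment at onset, which in this withdrawal crossover does not measure the randomised amifampridine-placebo safety contrast; the direction of the bias depends on an undefined start of treatment

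*Protocol*

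**What the plan says.** The first primary objective (Protocol 9.1) is "To characterize the overall safety and tolerability of amifampridine phosphate compared with placebo in patients with CMS".

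Protocol 11.1 defines events broadly: "a reportable AE is any untoward medical occurrence (e.g. sign, symptom, illness, disease or injury) in a patient administered the IP". It then lists what this includes, among them "AEs not previously observed in the patient that emerge during the course of the study" and "Pre-existing medical conditions judged by the investigator to have worsened in severity or frequency or changed in character during the study". Nothing there exempts CMS itself. Non-serious events are collected from the first dose of study drug, and Table 3 gives the starting point as Day 1 of run-in.

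For the analysis, Protocol 15.3 states "All treatment-emergent adverse events (TEAEs) will be summarized by the treatment at the time of onset", and SAP 5.0 repeats the rule. SAP 5.0 calls an event treatment-emergent if it occurs after treatment starts, without saying whether open-label or randomised treatment is meant. The shells for Tables 41 to 44 have amifampridine and placebo columns or parts (plus an overall one in Tables 42 to 44). The denominator is the safety population. There is no open-label column, no count of ongoing events and no marker for disease worsening.

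On the design, Protocol 8.5 says "This is a withdrawal study design looking at patient worsening on placebo". Under Protocol 10.1 patients have at least 7 days on a stable amifampridine dose before Period 1 and return to that dose on Days 9 to 21, before Period 2.

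**The concern.** Counting by onset works when patients start each treatment from a comparable untreated state. Here they do not. A patient entering a blinded amifampridine period continues the same dose, so a reaction already present does not begin in that period. A patient entering a placebo period is taken off an effective drug, and worsening of CMS then begins on placebo. Worsening of a pre-existing condition is reportable, so it counts as an event in the placebo column.

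The comparison protected by randomisation and blinding is whether an event is present under blinded amifampridine and absent under blinded placebo in the same patient. No planned table shows this. A reader of Tables 41 to 44 could misjudge tolerability in either direction, and could not separate loss of efficacy from adverse effects in the totals.

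**Working it through.** **Step 1: exposure behind each column.** The plan gives about 56 days per patient. By phase: run-in up to 28, Period 1 8, re-stabilization 13 (Days 9 to 21), Period 2 8. The sum is 28 + 8 + 13 + 8 = 57 (58 if re-stabilization is taken as 14 days, as the synopsis also states), which agrees with the plan.

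- If open-label days count: amifampridine 28 + 8 + 13 = 49 days, of which 41 are open-label, against 8 on placebo. The ratio is 49/8 = 6.1.
- With no run-in: 8 + 13 = 21 against 8, ratio 2.6.

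Both columns use the same patient denominator, with no exposure adjustment.

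**Step 2: what each start of treatment would count.** Inputs for illustration: N = 23 (synopsis), and a reaction rate of 20/46 = 43.5%, which reproduces the stated 43% for oral paresthesia in healthy volunteers given single 20 mg doses (Protocol 8.4.1). Assumptions: the rate carries over to CMS patients, and the reaction persists on a stable dose and clears on placebo. The share n of drug-naive patients is not stated, so it is varied.

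Affected patients: 23 × 20/46 = 10.0. Run-in onsets among the naive: 10n. If a reaction clears on placebo in Period 1 and returns in re-stabilization, and the return is recorded as an onset on amifampridine, the placebo-first half of the remaining patients is added: 10n + 10(1 − n)/2.

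| Counting rule | n = 0% | n = 50% | n = 100% |
|---|---|---|---|
| From randomisation, blinded-period onsets | 0 | 0 | 0 |
| From randomisation, plus recurrences in re-stabilization (half of 10) | 5 | 5 | 5 |
| From run-in Day 1 | 0 | 5 | 10 |
| From run-in Day 1, plus recurrences in the pre-treated | 5 | 7.5 | 10 |
| Present during blinded amifampridine | 10 | 10 | 10 |

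At the peripheral paresthesia rate of 12/46 = 26%, 23 × 12/46 = 6.0 patients are affected and every entry scales by 0.6.

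**Step 3: CMS worsening on placebo.** The documents give no rate. At assumed rates of 25%, 50% and 75%, 23 × rate = 5.75, 11.5 and 17.25 patients enter the placebo column.

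**Step 4: is the direction settled?** Further assumptions: on stable drug, 2% new non-disease onsets and 5% CMS worsening; on placebo, 5% other events and CMS worsening w of 20%, 35% or 50%; reaction rate 0.43.

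- Placebo: 23 × [1 − 0.95(1 − w)] = 5.5, 8.8, 12.1.
- Amifampridine, blinded onsets only: 23 × [1 − 0.98 × 0.95] = 1.6.
- Amifampridine, run-in onsets credited: 23 × [1 − (1 − 0.43n) × 0.98 × 0.95] = 6.2, 8.5, 10.8 for n = 50%, 75%, 100%.
- By presence, leaving out CMS worsening: 0.43 × 23 = 9.9 on amifampridine against 0.05 × 23 = 1.2 on placebo.

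With blinded onsets only, placebo is higher at every w. With run-in credited, amifampridine is higher at w = 20% for all three values of n, the order is mixed at w = 35%, and placebo is higher at w = 50%. The same inputs give either order, according to a definition that the SAP leaves open.

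**The case against.** The strongest reply is that the text of the plan is wider than the concern suggests. The list in Protocol 11.1 is inclusive, and the SAP definition contains no new-or-worsened test. A reader might infer that an established reaction can never be a treatment-emergent event. The documents do not support that: run-in onsets are collected, naive patients are titrated on study, and with a half-life of 1.8 hours (Protocol 8.5) a reaction can clear on placebo and return in re-stabilization.

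A reader might also infer that the rules favour the drug from both sides, or that the sign of the comparison reverses. Neither is established. If open-label days count, the amifampridine column has up to six times the exposure, which pushes the other way, and the reversal in Step 4 depends on the start date and on assumed rates.

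It is also fair that safety is descriptive in about 23 patients. Tables 42 to 44 break events down by preferred term and Table 44 by relationship, medical history is listed with an ongoing marker, and Data Listing 3 gives start and stop dates. Protocol 8.4.4 calls the common reactions typically transient, so persistence is an assumption. To say that loss of efficacy would simply be read as placebo toxicity is therefore too strong.

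These points limit the claim but do not answer it. None supplies the by-period contrast, and preferred terms do not repair the totals in Table 41. Protocol 8.4.4 itself notes that respiratory events reported with the drug are also symptoms of CMS, so the term alone cannot separate the two.

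**Conclusion.** The concern holds in this form: counting by onset does not give the randomised contrast named in the first primary objective, on either reading of the start of treatment.

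- **From randomisation:** a reaction present and persisting at Day 0 or Day 21 has no onset in the blinded amifampridine period that follows. It is counted only if a recurrence in re-stabilization is recorded and credited to the drug.
- **From run-in Day 1:** naive patients' reactions are counted, pre-treated patients' reactions may be missed unless they worsen or recur, and up to 49 mostly open-label days are compared with 8.
- **On either reading:** CMS worsening provoked by withdrawal enters the placebo column and is not shown separately.

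The direction of the bias depends on the undefined start and on the share of pre-treated patients, which is not stated. The size is not known from the documents. The 0 to 10 of about 10 affected patients in Step 2, and the placebo counts in Step 3, are illustrations that rest on a healthy-volunteer rate, on persistence of reactions and on assumed worsening rates. This is a worthwhile, inexpensive improvement to reporting; it does not touch the efficacy analysis.

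**What to change.** Keep the onset tables and add three things.

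1. State in SAP 5.0 when treatment starts for the treatment-emergent definition, and show run-in and re-stabilization onsets separately from blinded-period onsets.
2. Add a table, by treatment, of patients with any adverse event present, new or ongoing, in each blinded period (after the Day 0 visit to Day 8, and after the Day 21 visit to Day 29), using the dates in Data Listing 3. To support it, record suspected drug reactions already present at Day 0 as ongoing, and record their resolution or return at Days 8, 21 and 29. State how an event that stops within the first day of the switch is classed. The table compares equal 8-day periods and does not depend on the definition in item 1.
3. Mark CMS worsening on the adverse event form or, if data collection is too far advanced, classify it blind before unblinding. Print the totals of Tables 41 to 44 with and without it.

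The cost is one box on a form, a sentence in Protocol 11.1, some programming and extra table columns, and slightly more recording at Day 0. No extra visits or patients are needed.
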